## **CLINICAL TRIAL PROTOCOL SYNOPSIS**

Name of company: Boehringer Ingelheim	Tabulated Trial Protocol	
Name of finished product: Not applicable		
Name of active ingredient: BI 655130		
Protocol date: 08 March 2017	Trial number: 1368-0003	Revision date: Not applicable
Title of trial: Safety, tolerability, and pharmacokinetics of two dose strengths of a single subcutaneous dose of BI 655130 and one single intravenous dose of BI 655130 in healthy male and female subjects (open-label, parallel group design)		
Principal Investigator:		
Trial site:		
Clinical phase: I		
Objectives: To investigate safety, tolerability, and pharmacokinetics of two dose strengths of a single subcutaneous injection of BI 655130 and relative bioavailability of one strength of the subcutaneous formulation compared to an intravenous dose		
Methodology: Open-label, partially randomised design		
No. of subjects:  total entered: 36 each treatment: 12		
Diagnosis: Healthy subjects assigned to the intravenous dose will be matched for gender and body weight ( $\pm 10\%$ ) to subjects receiving the subcutaneous dose		
Main criteria for inclusion: Healthy male and female subjects, age of 18 to 50 years, body mass index (BMI) of 18.5 to 29.9 kg/m 		
Test product: BI 655130 solution for injection dose: and [Test] mode of admin.: Subcutaneous (SC) injection (perumbilical)		
Comparator product:  dose: mode of admin.: Intravenous (IV) as 30 min infusion		
Duration of treatment: One day (single dose) for each treatment		

Proprietary confidential information © 2017 Boehringer Ingelheim International GmbH or one or more of its affiliated companies

Name of company:		Tabulated Trial Protocol	
Boehringer Ingelheim			
Name of finished product:			
Not applicable			
Name of active ingredient:			
BI 655130			
Protocol date:	Trial number:		Revision date:
08 March 2017	1368-0003		Not applicable
Criteria for pharmacokinetics:	Primary endpoints: $AUC_{0-tz}$ and $C_{max}$ Secondary endpoints: $AUC_{0-\infty}$		

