## FLOW CHART

Single dose of BI 655130 as SC, SC or single IV infusion of of BI 655130 (subjects will receive only one dose)

Visit	Day	Time relative to first drug administration (planned time [h:min])	Approx. time (actual time) [h:min]	Event and comment	PK plasma 	Laboratory/ Urinalysis 	Body Temperature	Body Weight	12-lead ECG	ECG monitoring	Vital signs (BP, PR)	Query on adverse events, concomitant therapies 
1	-28 to -3			screening 		X		X	X		X	
2	-2	-48:00	8:00	ambulatory visit		X 						
2	-1	-12:00	20:00	admission to trial site		X 						X
1	1	-2:00	6:30		X 	X 	X 		X 		X 	X 
		0:00	8:00	drug administration start of infusion or SC injection						▲		
		0:30	8:30	▼ end of infusion 	X		X	X	—		X	X 
		1:00	9:00								X	
		1:30	9:30						X		X	
		2:00	10:00	light breakfast 	X		X	X	▼		X	
		2:30	10:30									
		3:00	11:00		X						X	
		4:00	12:00	Lunch 	X	X 					X	X 
		6:00	14:00				X	X			X	
		8:00	16:00	snack (voluntary) 	X						X	
		10:00	18:00	Dinner 								
		12:00	20:00		X		X	X			X	X 
	2	24:00	8:00	Breakfast 	X	X 	X		X		X	X 
		28:00	12:00	Lunch 								
		32:00	16:00	snack (voluntary) 			X				X	
		34:00	18:00	Dinner 								X 
3	48:00	8:00		Breakfast  discharge from trial site (confirmation of fitness) 	X				X		X	X 
4	72:00	8:00		ambulatory visit	X		X					X 
5	96:00	8:00		ambulatory visit	X							X 
6	120:00	8:00		ambulatory visit	X							X 
7	144:00	8:00		ambulatory visit	X							X 
8	168:00	8:00		ambulatory visit	X		X		X		X	X 
15	336:00	8:00		ambulatory visit	X							X 

Proprietary confidential information © 2017 Boehringer Ingelheim International GmbH or one or more of its affiliated companies

Visit	Day	Time relative to first drug administration (planned time [h:min])	Approx. time (actual time) [h:min]	Event and comment	PK blood 	Laboratory/ Urinalysis 	Body Temperature	Body Weight	12-lead ECG	ECG monitoring	vital signs (BP, PR)	Query on adverse events, concomitant therapies 
2	22	504:00	8:00	ambulatory visit	X	X			X		X	X

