### **3.3.4 Removal of subjects from therapy or assessments**

#### **3.3.4.1 Removal of individual subjects**

An individual subject is to be removed from the trial if:

1. The subject withdraws consent for trial treatment or trial participation, without the need to justify the decision
2. The subject needs to take concomitant drugs that interfere with the investigational product or other trial medication
3. The subject is no longer able to participate for other medical reasons (such as pregnancy, surgery, adverse events, or diseases)
4. An AE or clinically significant laboratory change or abnormality occurred that the investigator judges to warrant discontinuation of treatment. This may include cases of sustained symptomatic hypotension (BP <90/50 mmHg) or hypertension (BP >180/100 mmHg) or of clinically relevant changes in ECG requiring intervention as well as unexplained liver enzyme elevations at any time during the trial
5. The subject shows an elevation of AST and/or ALT  $\geq 3$ -fold ULN combined with an elevation of total bilirubin  $\geq 2$ -fold ULN (measured in the same blood sample) and/or marked peak aminotransferase (ALT and/or AST) elevations  $\geq 10$ -fold ULN and/or needs to be followed up according to the 'DILI checklist' provided in the ISF

In addition to these criteria, the physician may discontinue subjects at any time based on his or her clinical judgment.

Infusion reactions could also lead to the removal of an individual subject. However, in mild transient cases of infusion reactions (with clinical symptoms such as dizziness, headache, nausea) requiring no treatment, the clinical investigator may pause the infusion or continue with a reduced infusion rate as described for other therapeutic proteins [\[P16-06636\]](#). However, the overall infusion time (including time of discontinuation) must not exceed 45 minutes.

A subject can also be removed from the trial if eligibility criteria are being violated or if the subject fails to comply with the protocol (for instance, by non-adherence to dietary rules, or non-attendance at study assessments).

If a subject is removed from or withdraws from the trial prior to first administration of trial medication, the data of this subject will not be entered in the case report form (CRF) or trial database and will not be reported in the clinical trial report (CTR). If a subject is removed

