##### Intravenous infusion

Following an overnight fast of at least 10 hours, the medication will be administered. The infusion solution will be administered intravenously over 30 minutes. Start and time of the infusion will be recorded. Detailed handling instructions for the infusion will be provided in the ISF.

In case of safety concerns, e.g. due to infusion reactions, it is at the discretion of the investigator or his/her designee to adapt the infusion scheme, including but not limited slowing down the infusion rate, stopping of the infusion and, provided no further safety

Proprietary confidential information © 2017 Boehringer Ingelheim International GmbH or one or more of its affiliated companies

concern exist, restarting at a slower rate. Further, based on his/her medical judgment the investigator will provide medications such as steroids, etc. as needed.

For administration of the infusion, an intravenous indwelling catheter is placed into an arm vein of the subject and will be kept patent with a saline infusion. A second indwelling catheter used for collection of blood samples will be placed on the contralateral arm.

The administration of the trial medication will be done under supervision of the investigating physician or a designee. The so-called four-eye principle (two-person rule) should be applied for administration of trial medication and – if applicable – its preparation, if correct dosage cannot be ensured otherwise. For the purpose of drug accountability, the infusion set will be weighed before and after drug administration.

Subjects will be kept under close medical surveillance until 48 h following drug administration. For restrictions with regard to diet see [Section 4.2.2.2.](#)

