#### 6.2.2 Treatment period

Study participants will be admitted to the trial site in the evening of Day -1 and kept under close medical surveillance for at least 48 h following drug administration. The subjects will then be allowed to leave the trial site after formal assessment and confirmation of their fitness. On all other study days, the study will be performed in an ambulatory fashion.

Proprietary confidential information © 2017 Boehringer Ingelheim International GmbH or one or more of its affiliated companies

Details on treatments and procedures of administration are described in [Section 4.1.4](#).

For details on time points and procedures for collection of plasma samples for PK analysis, refer to [Flow Chart](#) and [Section 5.5.2](#).

The safety measurements performed during the treatment period are specified in [Section 5.2](#) of this protocol and in the [Flow Chart](#). For details on time points for all other trial procedures, refer to the [Flow Chart](#). AEs and concomitant therapy will be assessed continuously from screening until the end of trial examination.

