### **10.2.2 Infusion instructions**

In all patients, the infusion solution may be intravenously administered over a period of 1 hour. Infusion time can be extended up to 4 hours provided that the maximum time between the preparation and completion of administration of the solution to the patient does not exceed the 4 hours.

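### Appendix 10.2.2 allows a 1-hour IV infusion, extendable up to 4 hours; the rest of the protocol specifies 30 minutes, with 45 minutes the limit when an infusion is paused or slowed for mild transient reactions

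*Protocol*

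**What the plan says.** Three places in the protocol set the duration of the IV infusion at 30 minutes:

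- The synopsis, under the comparator product: "Intravenous (IV) as 30 min infusion".
- The Flow Chart, which starts the infusion at 0:00 and marks "end of infusion" in the 0:30 row.
- Section 4.1.4, Intravenous infusion: "The infusion solution will be administered intravenously over 30 minutes". For safety concerns, the same section lets the investigator slow, stop or restart the infusion and gives no time limit.

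Section 3.3.4.1 adds an upper limit. If an infusion is paused or slowed because of a mild, transient reaction that needs no treatment, "the overall infusion time (including time of discontinuation) must not exceed 45 minutes".

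Appendix 10.2.2, headed as infusion instructions and addressed to all patients, says something else: "the infusion solution may be intravenously administered over a period of 1 hour. Infusion time can be extended up to 4 hours". It attaches one condition to that extension: a 4-hour cap on the interval from preparation until the infusion is complete.

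Section 6.2.2 directs the reader to Section 4.1.4: "Details on treatments and procedures of administration are described in" that section. Section 4.1.4 in turn refers to the Flow Chart for timing. Neither says that the body takes precedence over the appendix.

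**The concern.** The IV arm is the reference treatment, and its administration instruction should be the same wherever a reader looks. A site that followed Appendix 10.2.2 would depart from the 30 minutes in the body even without using the extension. Section 4.1.8 requires medication to be given as the protocol specifies, and the appendix is part of the protocol, so the site could believe it was complying.

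Other timings in the IV arm depend on when the infusion ends. Section 4.2.2.2 counts the fast from the end of infusion, while the Flow Chart fixes the first meal by time from the start. Continuous ECG monitoring is described from the start of administration in one section and as a post-dose period in another. What is at stake is uniform conduct of the reference arm and agreement between infusion, meals and safety monitoring.

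**Working it through.** **1. Durations side by side**

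| Place in protocol | Duration | Condition |
|---|---|---|
| Synopsis; Flow Chart; Section 4.1.4 | 30 min | Standard infusion |
| Section 3.3.4.1 | At most 45 min overall | Paused or slowed for a mild transient reaction |
| Section 4.1.4 | No limit stated | Slowed, stopped or restarted for safety concerns |
| Appendix 10.2.2 | 1 h (60 min) | All patients, permissive |
| Appendix 10.2.2 | Extendable up to 4 h | At most 4 h between preparation and completion of administration |

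The unextended hour against the standard infusion: 60 / 30 = 2.

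Against the limit in Section 3.3.4.1: 60 − 45 = 15 min longer. That limit was written for one situation only, so this comparison is secondary. The 30-minute versus 1-hour conflict stands without it.

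**2. Fast and breakfast**

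Inputs: Section 4.2.2.2 bars food until 1.5 h after the end of infusion; the Flow Chart puts the "light breakfast" at 2:00 after the start.

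End of fast = infusion duration + 1.5 h.

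| Infusion | End of fast | Breakfast at 2:00 falls |
|---|---|---|
| 30 min | 0.50 + 1.5 = 2.00 h (2:00) | exactly at the end of the fast |
| 45 min | 0.75 + 1.5 = 2.25 h (2:15) | 15 min inside the fast |
| 1 h | 1.00 + 1.5 = 2.50 h (2:30) | 30 min inside the fast |

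The meal schedule therefore matches a 30-minute infusion and nothing longer. The mismatch already appears at the 45 minutes that Section 3.3.4.1 allows.

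**3. ECG monitoring**

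Section 5.2.4.2 describes continuous recording for 2 h from the start of infusion or injection, and the Flow Chart marks its end in the 2:00 row. Section 2.3 describes 1.5 h post dose. If post dose is counted from the end of infusion, a 30-minute infusion gives 0.5 + 1.5 = 2.0 h and the two descriptions agree; a 1-hour infusion gives 1.0 + 1.5 = 2.5 h and they do not. Only an infusion extended beyond 2 h could still be running when a 2-h recording stops.

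**4. Size of any effect on the primary endpoints**

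Assume one-compartment, linear kinetics and the half-lives of 20.4 to 33.9 days in Section 1.2.5, which the protocol itself calls estimates only. Relative to an instantaneous dose, the concentration at the end of an infusion of length T is

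f(T) = (1 − exp(−kT)) / (kT), with k = ln 2 / half-life.

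- Half-life 20.4 days: f(1 h) / f(0.5 h) = 0.99965, a change of −0.035%.
- Half-life 33.9 days: f(1 h) / f(0.5 h) = 0.99979, a change of −0.021%.
- At the outer bound of 4 h, the ratios to 30 minutes are 0.99753 and 0.99851, that is −0.25% and −0.15%.

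A distribution phase would make these changes larger. Under the same assumption, AUC extrapolated to infinity is dose divided by clearance and does not involve T.

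**The case against.** The best defence is that a site would be unlikely to follow Appendix 10.2.2. Its wording is permissive where Section 4.1.4 is directive. It speaks of patients in a trial of healthy subjects. It sits under a heading on preparation and handling. The body sends the site to Section 4.1.4 and the Flow Chart for administration, and to the investigator site file for preparation and handling. All of this is correct and lowers the chance of a 1-hour infusion. It does not remove the contradiction: 10.2.2 is itself headed as infusion instructions, it states an administration time, and no text subordinates it to the body.

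The defence is also right that the breakfast overlap does not arise from the appendix alone, since a 45-minute infusion already produces it. Deleting 10.2.2 would not cure that.

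Three stronger readings are tempting, and the documents do not support them:

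- **Monitoring would stop while drug is still running.** This needs an extension beyond 2 h. It also depends on whether the words *at least* in Section 5.2.4.2 govern the 2 h as well as the baseline period, and on what post dose means in Section 2.3. The Flow Chart mark at 2:00 favours a fixed end but does not settle it. Section 4.1.4 also requires supervised administration and close surveillance to 48 h.
- **The permitted infusion time is 4 h less the time taken to prepare the bag.** The interval between preparation and completion may equally be read as starting once the solution is ready, and the documents give no preparation time.
- **The relative bioavailability estimate is at risk.** Flow Chart footnote 14 ties the first post-infusion PK sample to completion of the infusion, and Section 5.5 uses actual sampling times. The changes calculated above are negligible.

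**Conclusion.** The contradiction is real and should be fixed. Appendix 10.2.2 permits, for all patients, an infusion twice as long as the one specified in the synopsis, Flow Chart and Section 4.1.4. It is also longer than the 45 minutes allowed by Section 3.3.4.1 for an infusion interrupted or slowed by a mild transient reaction. This rests on the text alone and needs no assumption.

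The 30-minute overlap of breakfast with the fast at 1 h follows directly from Section 4.2.2.2 and the planned times in the Flow Chart. The ECG consequence is conditional on an extension beyond 2 h and on the reading of Sections 2.3 and 5.2.4.2. No material effect on Cmax or AUC is claimed; that statement rests on the one-compartment assumption and the protocol's half-life range. The point concerns consistent administration and monitoring in the reference arm, not the validity of the primary analysis. No view is taken on which duration is right.

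**What to change.** Reconcile the synopsis, the Flow Chart, Sections 3.3.4.1 and 4.1.4 and Appendix 10.2.2 so that one infusion duration and one upper limit apply throughout. Then check that the fasting rule (Section 4.2.2.2), the meal times (Flow Chart) and the ECG monitoring period (Flow Chart, Sections 2.3 and 5.2.4.2) agree with those values across the whole permitted range. The sponsor's clinical team decides the values.

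The cost is a wording correction to the protocol, with no added procedure or subject. The SAP can stay as it is: Section 6.2 already takes deviations in drug administration to the report planning or database lock meeting, and Sections 5.4.2 and 7.3 already derive and summarise infusion duration in the IV group.

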**10.2.3 Preparation Instructions SC dose**

**Necessary materials:**

1 Vial BI 655130 Solution for Injection

**Consumables:**

sterile polypropylene syringe - e.g. B. Braun Injekt F (article no: 9166017V)

1 x 21G 1½" needle (material: stainless steel/ polypropylene) – e.g. B. Braun (article no 4657527)

1 x 30G ½" needle for injection (material: stainless steel/ polypropylene) – e.g. BD (article no: 304000)

1. Take a vial filled with of BI 655130 Solution for Injection to BI 655130 Solution for Injection out of the refrigerator and let it reach room temperature for 30 minutes.
2. Gently invert the vial five times to homogenize prior to use. Check the vial content for visible particles. The solution should be colorless to slightly brownish-yellow and clear to slightly opalescent. If discoloration or visual particles are seen discard the vial.
3. Remove the protective cap from the vial.
4. Using appropriate aseptic technique, insert a sterile 21G needle through the center of the stopper and withdraw the complete content of the vial. using a sterile syringe
5. In case the medication will not be injected immediately close the syringe with a Combi-Stopper.
6. Attach a sterile 30G ½" needle to the syringe, adjust the volume to and gently inject the complete content of the syringe.

**10.2.4 Preparation Instructions SC Dose**

**Necessary materials:**

2 Vials BI655130 Solution for Injection

**Consumables:**

sterile polypropylene syringe - e.g. B. Braun Injekt Solo (article no: 4606027)

needle (material: stainless steel/ polypropylene) – e.g. B. Braun (article no 4657527)

needle for injection (material: stainless steel/ polypropylene) –  
e.g. BD (article no: 304000)

1. Take two vials filled with of BI 655130 Solution for Injection out of the refrigerator and let it reach room temperature for 30 minutes.
2. Take the first vial and gently invert the vial five times to homogenize prior to use. Check the vial content for visible particles. The solution should be colorless to slightly brownish-yellow and clear to slightly opalescent. If discoloration or visual particles are seen discard the vial.
3. Remove the protective cap from this vial.
4. Using appropriate aseptic technique, insert a sterile 21G needle through the center of the stopper and withdraw the complete content of this vial using a sterile syringe.
5. Repeat steps 1 to 4 with the second vial using the syringe already filled with
6. In case the medication will not be injected immediately close the syringe with a Combi-Stopper.
7. Attach a sterile needle to the syringe, adjust the volume to and gently inject the complete content of the syringe.

## **11. DESCRIPTION OF GLOBAL AMENDMENT(S)**

This is the original protocol.

Number of global amendment		
Date of CTP revision		
EudraCT number		
BI Trial number		
BI Investigational Product(s)		
Title of protocol		
<hr/>		
To be implemented only after approval of the IRB / IEC / Competent Authorities		
To be implemented immediately in order to eliminate hazard – IRB / IEC / Competent Authority to be notified of change with request for approval		
Can be implemented without IRB / IEC / Competent Authority approval as changes involve logistical or administrative aspects only		
<hr/>		
Section to be changed		
Description of change		
Rationale for change		

## **2. LIST OF ABBREVIATIONS**

Term	Definition / description
ADPC	Proper name of the analysis dataset containing PK concentrations per time-point or per time-interval
ADPP	Proper name of the analysis dataset containing calculated PK parameters
ADS	Analysis dataset
AE	Adverse event
AESI	Adverse event of special interest
ALT	Alanine aminotransferase
ANOVA	Analysis of variance
AST	Aspartate aminotransferase
AUC 0-∞	Area under the concentration-time curve of the analyte in plasma over the time interval from 0 extrapolated to infinity
AUC 0-tz	Area under the concentration-time curve of the analyte in plasma over the time interval from 0 to the last quantifiable data point
BI	Boehringer Ingelheim
BLQ	Below the lower limit of quantification
BMI	Body mass index
CARE	Clinical data analysis and reporting environment
CI	Confidence interval
Cmax	Maximum measured concentration of the analyte in plasma
CRF	Case Report Form
CTP	Clinical Trial Protocol
CTR	Clinical Trial Report
CV	Arithmetic coefficient of variation
DBLM	Database lock meeting
ECG	Electrocardiogram
eCRF	Electronic case report form
ER	Exploratory reference treatment
EudraCT	European union drug regulating authorities clinical trials
gCV	Geometric coefficient of variation

Term	Definition / description
gMean	Geometric mean
ICH	International Conference On Harmonisation
IPV	Important protocol violation
MedDRA	Medical Dictionary For Regulatory Activities
NOA	Not analysed
NOR	No valid result
NOS	No sample available
on-trt	on-treatment
PK	Pharmacokinetics
PKS	Pharmacokinetic parameter analysis set
PV	Protocol Violation
Q1	Lower Quartile
Q3	Upper Quartile
R	Reference treatment
RAGe	Report appendix generator
RPM	Report Planning Meeting
SAE	Serious adverse event
SD	Standard Deviation
SDL	Subject data listing
SOC	System Organ Class
T	Test treatment
TSAP	Trial Statistical Analysis Plan
ULN	Upper limit of normal range

### **3. INTRODUCTION**

As per ICH E9 ([1](#)), the purpose of this document is to provide a more technical and detailed elaboration of the principal features of the analysis described in the CTP, and to include detailed procedures for executing the statistical analysis of the primary and secondary variables and other data.

This TSAP assumes familiarity with the CTP. In particular, the TSAP is based on the planned analysis specification as written in CTP Section 7 "Statistical Methods and Determination of Sample Size". Therefore, TSAP readers may consult the CTP for more background information on the study, e.g., on study objectives, study design and population, treatments, definition of measurements and variables, planning of sample size, randomisation.

Study data will be stored in a trial database within the Oracle ClinicalTM system.

The statistical analyses will be performed within the validated working environment CARE, including SASTM (current Version 9.4, by SAS Institute Inc., Cary, NC, USA), and a number of SASTM-based tools (e.g., macros for the analyses of AE data or laboratory data; Report Appendix Generator system (RAGe) for compilation/formatting of the CTR appendices).

PK parameters will be calculated using Phoenix WinNonlinTM software (version 6.3, Certara USA Inc., Princeton, NJ, USA).

